- For patients randomized to the control group: o The Dexcom G6 sensor will be removed and other parts i.e., receiver and transmitter, collected.
 - The patient will be reminded of the installation of a CGM for 20 days at Day 70.
 The patient will be provided with the schedule of visits at home and at the hospital, with the patient diary
- For patients randomized in the investigational group: Pump will be installed.
 - Patient visit will include 2 nights at hospital for patient observation following the set-up of the Dexcom G6 CGM system with the Pump in open mode.
 - The patient (and the caregiver if applicable) will be trained to the use of the Pump and CGM in open mode, specifically on the management of alarms or alerts on the pump and on meal information entry into the pump for bolus insulin delivery (always the same value to facilitate the entry and avoid carbohydrate calculation). Patients will be provided with a short notice describing the management of meals announcement before leaving hospital.
 - After 48h of observation, the Investigator will ensure that the patient (or the caregiver) is able to go back home and follow the instructions for study continuation, and plan the date of the next visit at the hospital to initiate the

Run-in period. Otherwise, the patient will be withdrawn from the study and replaced.

- The patient will be reminded of the next steps of the protocol and will be provided with the schedule of visits at home and at the hospital, with the patient diary
- The investigator will fill in the e-CRF.
- During the next weeks, the investigator will have access to patient's glycaemic data through the cloud-based t:connect® platform and will be trained by the HHP to the display and exploitation of data on the t:connect® platform. The investigator will receive the report from the HHP following his/her visit at patient home.
- o After Visit 1, the investigator will complete the e-CRF

VI.3.2 - ROLES OF THE HOME HEALTHCARE PROVIDER (HHP)

Patients randomized in the control group:

- The HHP will attend the visit at the hospital to collect the Dexcom G6 CGM devices, the dedicated laptop and fill the related certificate.
- The HHP will contact the family nurse to plan the date for the installation of the Dexcom G6 CGM system at Day 70 at the patient's home.
- The HHP will remind the patient to report adverse events and/or device deficiencies/failure in the patient diary.

Patients randomized in the investigational group:

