For patients of the investigational group:

- The family nurse(s) will be trained to the use of the Tandem t:slim X2 with control IQ technology system and to the upload of data and to data visualisation on the t:connect® platform.
- The family nurse will administer the insulin bolus during his (her) visit at the patient's home
 using the Tandem t:slim X2 insulin pump as instructed during his (her) training. The frequency
 of the daily home nurse visit(s) will remain the same as for standard diabetes care during the
 initiation period.
- The family nurse will replace the catheter and refill the insulin cartridge of the Pump every 3 days at home.
 - The family nurse will change and replace the Dexcom G6 sensor every 9 days and upload the Dexcom G6 CGM and pump data on the cloud-based t:connect® platform.
- The family nurse will be reminded of the date of the next visit at the hospital and of the procedures to be performed until then.
- During each visit at the patient's home, the family nurse will ensure that any adverse events and device failure/deficiencies will be reported by the patient in his/her diary. The family nurse will immediately inform the HHP nurse of any adverse events or device deficiencies/failure occurring during the trial.

VI.4 - Run-In visit (V2)

The run-in visit purpose will be to finalize the installation of the automated insulin delivery system studied in the investigational group. Thus, this visit will be the starting point of the evaluation of the tested strategy CONFIDENTIAL Restricted- Clinical Investigation Plan version n° 7.0 – 04/03/2025 69 / 155

therapy. The run-in visit is performed at the hospital **for patients of the investigational group only**. It will consist in a 2-night hospitalization for the automated insulin delivery system to be initiated (closed-loop mode), the settings adjusted and the patient trained to the management of the automated insulin delivery system in closed-loop mode.

VI.4.1 - ROLES OF THE INVESTIGATOR

- The Investigator will be trained to the automated insulin delivery system in closed-loop mode and to the display and exploitation of data on the t:connect® platform.
- The Investigator will set up the automated insulin delivery system and define the settings based on insulin pump and CGM data collected during the initiation period, using the standard mode of the algorithm. The patient will be closely monitored to ensure the settings and mode chosen are safe.

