 Blood counts (Red Blood Cells (RBC), White Blood Cells (WBC), platelets, haemoglobin, and hematocrit).

VI.7.1.8 - GLYCAEMIC CONTROL AND GLYCAEMIC VARIABILITY

In addition to HbA1c assays, the glycaemic control and variability will be computed based on the continuous measurement of the glucose values recorded after wearing the CGM device in blinded mode during the 14 consecutive days of the selection period and every day from D70 to D90.

VI.7.1.9 - Adverse Events/Device Deficiencies/Failure

Safety assessments will consist in evaluating all serious and non-serious adverse events (AE), and device deficiencies/failure occurring from the Informed Consent Form (ICF) signature until the end of the study.

At each visit, occurrence of AEs and device deficiencies/failure should be inquired and follow-up of previously reported AEs and device deficiencies/failure should be performed. Related essential data should be recorded in the patient's medical file and in the e-CRF by the Investigator.

For the AEs, the following data will be recorded in the e-CRF:

[figure not shown]
- Description of the AE
- Seriousness of the event
- Onset and resolution dates of the AE
- Severity of the AE (mild, moderate or severe)
- Causality with regards to IMD
- Causality with regards to investigation procedures
- Action(s) taken regarding the IMD Corrective treatment/therapy given Event outcome.

In addition, the following parameters will be considered for assessment of the safety profile of automated insulin delivery system:

[figure not shown]
- Hypoglycaemic events defined as at least 10 min of continuous CGM readings below the thresholds of (1) 70 mg/dL (3.9 mmol/L) or (2) 54 mg/dL (3.0 mmol/L),
- Non severe hypoglycaemic events, being defined by CGM readings between < 70 mg/dL (3.9 mmol/L) and ≥ 54 mg/dL (3.0 mmol/L),
- Severe hypoglycaemic events being defined by CGM readings < 54 mg/dL,
- Severe hypoglycaemic events requiring third party assistance,
- Severe hypoglycaemic events requiring hospitalization,
- Severe hyperglycaemic events being defined by CGM readings ≥ 300 mg/dL for over 1 hour, Device incidents and deficiencies.

A Data Safety Monitoring Board (DSMB) will review the safety data of the five first patients of each group, then 25 patients having completed the study, and more frequently if judged necessary by the DSMB.

[figure not shown]

[figure not shown]

VII - ENDPOINTS

VII.1 - PRIMARY ENDPOINT

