- Number of severe nocturnal hypoglycaemic events (i.e., occurring from 00.00 H to 05.59 H)
- Number of severe hypoglycaemic events requiring third party assistance
- Number of severe hypoglycaemic events requiring hospitalization
- Number of severe hyperglycaemic events (≥ 300 mg/dL for over 1 hour).

[figure not shown]
Adverse events and device deficiencies/failure will be collected from the signature of the informed consent to study end.

A Data Safety Monitoring Board (DSMB) will review the safety data of the five first patients of each group, then 25 patients having completed the study, and more frequently if judged necessary by the DSMB.

Composition, role and frequency of DSMB meetings will be detailed in the separate DSMB Charter.

VII.3.2 -

VIII - SAFETY AND DEVICE DEFICIENCIES

VIII.1 - DEFINITIONS

Adverse Event (AE)

Any untoward medical occurrence, unintended disease or injury, or untoward clinical signs (including clinically significant abnormal laboratory findings) in patients, users or other persons, whether or not related to the investigational medical device.

This definition includes events related to the procedures involved (see definition below).

For users or other persons, this definition is restricted to events related to investigational medical devices.

Investigation Procedure

Any procedure specific to the clinical investigation. All activities related to the use of a medical device may be considered investigation procedures.

Note: "Preceding investigation procedure" shall be understood as a procedure which is imposed by the Clinical Investigation Plan and which has taken place before (or coincided in time) with the serious adverse event.

Adverse Device Effect (ADE)

Adverse Event related to the use of an investigational medical device.

This definition includes adverse events resulting from insufficient or inadequate instructions for use, deployment, implantation, installation, or operation, or any malfunction of the investigational medical device.

This definition includes any event resulting from use error or from intentional misuse of the investigational medical device.

Abnormal laboratory value

All abnormal laboratory values that the investigator is aware of will be reported as Adverse Events if the investigator categorizes their values as « Clinically Significant » (CS).

Serious Adverse Device Effect (SADE)

Adverse Device Effect that has resulted in any of the consequences characteristic of a Serious Adverse Event.

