Each secondary efficacy endpoint will be summarised at each time point using descriptive statistics and compared between study groups using Cochran-Mantel-Haenszel chi-squared tests adjusted on the HbA1c level at baseline (2-categories stratification variable) or analyses of covariance with or without repeated measures (depending on the analysed parameter and its frequency of collection in both study groups) adjusted on the HbA1c level at baseline.

When appropriate, analyses based on CGM measures will be performed considering (1) the full 24-h day, (2) diurnal period (from 06.00 H to 23.59 H) and (3) nocturnal period (from 00.00 H to 05.59 H) separately.

When relevant, continuous, longitudinal endpoint data (e.g. HbA1c, Total daily insulin dose, body weight) will be analysed using the mixed effects model for repeated measures method based on the restricted maximum

likelihood for estimation with several prespecified fixed effects, including first-order interactions with time, and the corresponding endpoint as the dependent variable in the model. ANCOVA will be used for analyses of measures taken at a single time point post baseline in both study groups.

X.3.5 - SAFETY EVALUATION

Safety data will be tabulated descriptively by study group and assessment time, when relevant. Extent of exposure and Adverse Events will be tabulated in the Randomised ITT and the safety data sets (defined in section X.2.1). No statistical test will be performed.

X.3.5.1 - EXTENT OF EXPOSURE

Duration of the 4 study periods (Selection, Initiation, Run-in and Follow-up periods) and overall study duration will be tabulated (expressed in days) by study group (and globally), as both quantitative and categorical data.

Overall study duration is defined as the time interval between the actual date of the selection visit (*VO included*) and the actual date of the end of study visit (*V9 excluded*) whether the end of study occurred at the time of premature withdrawal or on visit date corresponding to D90 as planned, i.e., as the time interval equal to "date of end of study visit (V9) - date of selection visit (V0)".

X.3.5.2 - ADVERSE EVENTS (AES)

The time period for the recording of Adverse Events (AEs) is the time interval between selection (V0) and end of study (V9) divided in 2 periods, either before or after the initiation visit (V1). All reported AEs will be classified in one of these 2 periods, according to their start date.

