AEs tabulated evaluations described below will be performed on Study Emergent Adverse Events (SEAEs). AEs occurring before the initiation visit (V1) will be tabulated in the Randomised ITT and the safety data sets separately, if relevant, or they will be listed if too few patients are concerned.

Each AE (whether serious or not serious, according to their regulatory definition provided in section VIII.1) having been reported throughout the study for a given patient will be classified by Preferred Term (PT) and corresponding primary System Organ Class (SOC), using the MedDRA terminology, prior to the study database lock.

An AE will be categorised as Study Emergent if it begins at the earliest on the day of the initiation visit (V1). In case of missing or partial AE start date, an AE will be considered as Study Emergent (SE):

- (1) if the AE start date is unknown,
- or (2) if the partial AE start date is on or after the date of the initiation visit (V1) (i.e., 'year' or 'year and month' is/are 'the same as' or 'after' those of the date of Visit 1).

An overall summary of AEs will be provided by study group, including:

- the number and percentage of patients with at least 1 AE and the total number of AEs,
- the number and percentage of patients with at least 1 SEAE and the total number of SEAEs,
- the distribution of the number of SEAEs reported by patient (in 5 categories, if relevant: 1 SEAE, [2 3] SEAEs, [4 6] SEAEs, [7 9] SEAEs or 10 or more SEAEs),
- the number and percentage of patients with at least 1 Serious SEAE and the total number of Serious SEAEs,

- the number and percentage of patients with at least 1 possibly IMD related SEAE (possibly IMD related SEAEs being defined as SEAEs for which the investigator has reported at least once either 'Causal relationship' or 'Probable' or 'Possible' for the relationship to the IMD) and the total number of those possibly IMD related SEAEs,
- the number and percentage of patients with at least 1 SEAE possibly related to investigation procedures (SEAEs possibly related to investigation procedures being defined as SEAEs for which the investigator has reported at least once either 'Causal relationship' or 'Probable' or 'Possible' for the relationship to the investigation procedures) and the total number of those SEAEs possibly related to investigation procedures,
- the number and percentage of patients with at least 1 AE leading to study premature withdrawal and the total number of those significant AEs.

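### The Study Emergent definition goes by start date alone, so an adverse event that begins in selection and worsens after V1 drops out of the SEAE tables

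*Combined protocol and SAP*

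**What the plan says.** Collection starts well before V1. Section VII.3.1 states: "Adverse events and device deficiencies/failure will be collected from the signature of the informed consent to study end". Selection includes 14 to 28 days of blinded CGM in every patient (VI.2), and the CGM is one of the two investigational devices (V.1).

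Section X.3.5.2 splits the record into a period before V1 and a period after it: "All reported AEs will be classified in one of these 2 periods, according to their start date". The definition follows: "An AE will be categorised as Study Emergent if it begins at the earliest on the day of the initiation visit (V1"). The main outputs depend on it: "AEs tabulated evaluations described below will be performed on Study Emergent Adverse Events (SEAEs"). Earlier events go elsewhere: "AEs occurring before the initiation visit (V1) will be tabulated in the Randomised ITT and the safety data sets separately", or they are listed if few patients are concerned.

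For timing, the e-CRF items in VI.7.1.9 give "Onset and resolution dates of the AE". Severity and seriousness are also listed. No date of worsening or of becoming serious appears, and neither VI.7.1.9 nor VIII.2.1 says that a worsening is entered as a new event.

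At V1 the control group stops CGM: "The Dexcom G6 sensor will be removed and other parts i.e., receiver and transmitter, collected" (VI.3.1). It wears a sensor again from D70. The investigational group receives a new sensor and the pump at V1, and for the initiation period VI.3.3 says: "The family nurse will change and replace the Dexcom G6 sensor every 9 days".

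**The concern.** The SEAE tables are the plan's main by-arm description of safety once the two strategies diverge. A usual treatment-emergent definition includes events that start earlier and get worse under treatment, so that an aggravation is not hidden behind an old onset date. This definition has no such clause.

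If a site updates the severity on the existing record, the upgraded event keeps its pre-V1 start date. The event is then absent from the post-V1 tables, and the pre-V1 table or listing shows a severity that arose only after the strategies began. That is misplacement as well as omission.

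The rest of the safety plan is more inclusive. An AE with an unknown start date counts as Study Emergent, and laboratory values get changes from V1 and a shift table. AEs alone have no means of showing deterioration from V1.

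**Working it through.** The plan states no figure for this point, so the check is mainly of text: follow each kind of event through the rules of X.3.5.2.

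| Event | Start date | In SEAE outputs? | Where else it appears |
|---|---|---|---|
| Pump-site reaction | On or after V1, since the pump is first fitted there | Yes | – |
| Selection event that resolves, with a new episode after V1 | New date, after V1 | Yes; repeats of one term are merged only within a period | Pre-V1 output for the first episode |
| Selection event, continuous, unchanged | Before V1 | No, and rightly so | Pre-V1 output |
| Selection event, continuous, becomes serious after V1 | Before V1 | No | SAE listing from V0; list and table of unplanned hospitalisations if admitted; withdrawal row if it leads to withdrawal |
| Selection event, continuous, device-related, worsens but stays non-serious | Before V1 | No | Listing of Adverse Device Effects, if relevant; no by-arm percentages |
| Selection event, continuous, not device-related, mild to severe, no withdrawal | Before V1 | No | Pre-V1 output and the all-AE row only |

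The last three rows are the gap. The SEAE outputs affected are the any-SEAE, Serious, device-related and procedure-related rows, and the tables by organ class and term, most severe intensity and worst relationship.

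One ambiguity bears on the fourth row. The overall summary is repeated for SAEs, and a table of SAEs by organ class and term is planned. Both say SAE rather than Serious SEAE, yet the opening sentence of the section puts the evaluations below it on SEAEs. Whether these two outputs would include the event cannot be settled from the text.

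**Scale.** The denominator is the 28 randomised per group in X.1. It reproduces: 2 × (16/17)² × (1.960 + 1.282)² = 18.6; × 1.10 = 20.5, rounded up to 21; 21/0.75 = 28, or 56 in total.

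- One patient left out of a row: 1/28 = 3.6 percentage points of an arm. Two: 2/28 = 7.1.
- The most-common-SEAE table uses a 5.0% cut: 0.05 × 56 = 2.8, so 3 patients (3/56 = 5.4%) qualify and 2 (2/56 = 3.6%) do not, if all 56 are in the safety set. One omission can remove a term.

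**Illustration on assumed rates.** The documents give none. Let p be the share of an arm with an AE ongoing at V1, and q the share of those that worsen. The expected number omitted per arm is 28pq, and the chance of at least one is 1 − (1 − pq)^28.

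- p = 5%, q = 10%: 28 × 0.005 = 0.14 patients; chance 0.13.
- p = 10%, q = 30%: 28 × 0.03 = 0.84 patients; chance 0.57.
- p = 20%, q = 50%: 28 × 0.10 = 2.8 patients; chance 0.95.

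**The case against.** The strongest reply is that little is lost, and it is largely right about serious and device-related events. All SAEs are listed from V0 with individual detail. Adverse Device Effects are listed with no cut at V1. AEs leading to withdrawal have their own row, and unplanned hospitalisations are tabulated by group. A reader might infer that events turning serious on the device vanish from the safety reporting; they do not.

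A reader might also infer that the rule hides harm mainly in the device arm and so favours the device. The documents do not support that:

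- Under VI.2.2 the selection CGM comes off at the initiation visit without distinction of arm, and VI.3 gives device patients a new sensor. A reaction to a later sensor would normally be a new event with a post-V1 date.
- Pump-site reactions cannot begin before V1, so the existing rule already counts them.
- Patients must be judged able to wear a CGM safely before randomisation, which makes a persisting sensor reaction less likely.
- Control patients' ongoing events can worsen too, and their insulin may be adjusted at V1.

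Finally, the e-CRF may handle worsening. X.3.5.2 refers to relationships reported at least once and to the worst recorded relationship, which could mean repeated assessments per event. If sites open a new record at worsening, the present definition already captures it. No section gives that instruction, however, so this does not close the gap. A non-serious event going from mild to severe after V1 without withdrawal still reaches no by-arm post-V1 table.

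**Conclusion.** The point holds in a narrow form. By its stated rule, X.3.5.2 excludes from all SEAE outputs a continuous AE that begins in selection and increases in severity or becomes serious after V1. The main loss is non-serious worsening from the by-arm post-V1 comparison; the graver cases surface in other outputs.

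The number of patients is unknown and probably small. The illustrative 0.14 to 2.8 per 28-patient arm rests wholly on assumed rates. In arms this small, though, one patient moves a row by 3.6 points. The gap can occur in either arm. A higher frequency in the device arm is plausible only for device-type events, because CGM use continues there after V1 while control patients are without a sensor until D70; it is not shown.

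The conclusion assumes that worsening is updated on the existing AE record, which the documents neither state nor rule out. Safety is descriptive with no test, so neither sample size nor type I error is affected.

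**What to change.** 1. In X.3.5.2, define an SEAE as an AE that begins on or after the day of V1, or that began earlier and increased in severity or became serious on or after that day. Apply the same rule to the period classification.
2. In VI.7.1.9 and VIII.2.1, have sites record the date of that change, or open a new AE entry at worsening with its own onset date. Choose one route and state it. A new entry would already fall under the present definition, but only if sites are told to make it.
3. State whether the SAE summary and the SAE table by organ class and term use all SAEs or only Serious SEAEs.

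The cost is one sentence in the analysis text, one clarification of the SAE tables and one e-CRF completion instruction, with a few more entries and slightly higher SEAE counts. Section X.3 has the final SAP approved after the Data Review Meeting and before analysis, so the wording can still be added there. The date of change is better collected prospectively; for records already entered it would have to be queried.

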In the event of any deficiency of one or more of the components of the automated insulin delivery system, the patient should have immediate access to a first aid kit including replacement therapy (fast-acting insulin and insulin pen).

Of note, acetaminophen is compatible (up to 1 g every 6 hours) with the study automated insulin delivery system.

VI - SCHEDULE OF ASSESSMENTS

VI.1 - STUDY FLOWCHART

Ten visits are planned in the study:

- A Selection visit (Visit 0)
- An Initiation visit (Visit 1)
- A Run-In visit (Visit 2)
- Six follow-up visits over a 3-month period (Visits 3 to 8) An end of study visit (Visit 9).

The study flowchart is available and presented in Figure 1 and Figure 2 with detailed contents per study group allocated.

VI.2 - SELECTION VISIT (V0) AND SELECTION PERIOD

The selection will include two different steps: the patient will first be invited to participate in the trial during a consultation visit to his (her) diabetes specialist, performed at hospital. The second step consists of a 14-to 28-day blinded continuous glucose monitoring period at patient's home, including regular home visits performed by the HHP and the family nurse. Each step of this selection period is detailed below according to the healthcare professional in charge of its performance.

VI.2.1 - ROLES OF THE INVESTIGATOR

Before any inclusion, the Investigator will be trained to the use of the automated insulin delivery system by the HHP.

- At patient's selection visit (Visit 0), the Investigator will:
 - Perform a first verification of selection, inclusion and exclusion criteria to check the potential eligibility of the patient to the study, including resource person details for isolated patients.
 - Give an overview of the protocol to the patient. If the patient is interested in participating in the trial, the automated insulin delivery system will be presented and the different periods of the trial explained in detail to the patient and caregiver (if applicable).
 - Give the information letter to the patient and the patient will sign the informed consent form if he/she agrees to participate.
 - Perform the following evaluations:
 - Blood pregnancy test for women of child-bearing potential.
 - Review of the current treatment(s) including T2D treatments and nonauthorized concomitant medication (as mentioned in section V.8).
 - Physical examination including cognitive assessment (MoCA and/or MMSE), blood pressure, body weight and height.

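### The missing-date rule in X.3.5.2 ignores the recorded resolution date, so an adverse event known to have ended before V1 can be counted as Study Emergent

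*Combined protocol and SAP*

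**What the plan says.** Section X.3.5.2 splits the recording period in two at V1: "All reported AEs will be classified in one of these 2 periods, according to their start date". For a complete start date the definition is clear: "An AE will be categorised as Study Emergent if it begins at the earliest on the day of the initiation visit (V1").

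For incomplete dates the same section says: "In case of missing or partial AE start date, an AE will be considered as Study Emergent (SE"). Two branches follow. The first applies "1) if the AE start date is unknown". The second applies to a partial date where "year' or 'year and month' is/are 'the same as' or 'after' those of the date of Visit 1". Neither branch has a condition on the end date, and no exception appears elsewhere in the protocol.

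Three other provisions bear on the point:

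- Section VI.7.1.9 covers events "occurring from the Informed Consent Form (ICF) signature until the end of the study", so collection starts well before V1.
- The e-CRF fields in that section include "Onset and resolution dates of the AE".
- Section VI.2 places a "14-to 28-day blinded continuous glucose monitoring period at patient's home" before V1, so there is time for an event to begin and end before that visit.

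The SEAE class is the basis for the tables by SOC and PT, by intensity, and by relationship to the device and to investigation procedures. Events before V1 are tabulated or listed separately.

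**The concern.** An event that ended before V1 cannot have begun on or after V1. When the resolution date is on file and precedes V1, the timing is not in doubt, whatever is missing from the start date. The rule still assigns the event to the post-V1 class, so it contradicts the definition given just before it.

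Two outputs are affected. The SEAE tables may gain an event that does not belong there, and the pre-V1 tabulation loses it. Two identical events can also fall in different periods only because one has a complete start date and the other does not.

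**Working it through.** The plan states no figure on this point, so there is nothing to reproduce. The check is to apply the rule as written to test records.

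**Inputs.** Definition and both branches: X.3.5.2. Resolution date available: VI.7.1.9. Planned group size 28: X.1. The dates are illustrative: V1 on 20 June 2022 and resolution on 10 June 2022, ten days before V1.

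| Start date recorded | Rule as written | With an end-date check |
|---|---|---|
| Unknown | Study Emergent | Before V1 |
| 2022 (year only) | Study Emergent | Before V1 |
| June 2022 (day missing) | Study Emergent | Before V1 |
| May 2022 (day missing) | Before V1 | Before V1 |
| 2021 (year only) | Before V1 | Before V1 |
| 8 June 2022 (complete) | Before V1 | Before V1 |

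The event ended on 10 June in every row, so the correct class is always before V1. The rule is wrong in the first three rows. The end-date check corrects those three and leaves the others unchanged. Year-only dates in V1's year are affected as well as dates that lack only the day.

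**Upper limit per patient.** At the planned group size, one patient wrongly counted as having at least one SEAE adds 1/28 = 0.0357, or about 3.6 percentage points, to that group's incidence. Two conditions limit this:

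- For the overall row, the patient must have no other SEAE. Follow-up from V1 is about 15 weeks in the investigational group and about 12 weeks in the control group (V.6).
- For a Preferred Term row, the patient must have no event of the same term after V1, because X.3.5.2 counts recurrences of a term once per patient and period.

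The SOC and PT tables use the safety set, meaning randomised patients still in the study at the end of V1 (X.2.1). The denominator may therefore differ from 28.

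**The 5.0% list.** X.3.5.2 calls an SEAE most common if it occurs in at least 5.0% of the safety set. With 56 patients, 0.05 × 56 = 2.8, so three patients are needed. One misplaced patient could move a term from 2/56 = 3.6% to 3/56 = 5.4%, subject to the same condition on that term.

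**What cannot be computed.** The documents do not say how many events will have incomplete start dates, or how many of those will have an end date before V1.

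**The case against.** The case for leaving the rule alone has substance. Treating an event of uncertain timing as emergent is a conservative convention that errs towards over-counting harm. The rule is the same in both groups, and X.3.5 says that no test will be done on safety data. Incomplete dates should be uncommon: the family nurse checks the diary during selection (VI.2.3), the home healthcare provider reports events before randomisation (VI.2.2), the investigator reviews the diary at V1 (VI.3.1), and monitors compare the e-CRF with source (IX.1, XI). SAEs, events leading to withdrawal and, if relevant, adverse device effects are listed individually with timing and duration, so a misplaced event of those kinds would be visible. A separate SAP is planned (X.3) and may add the check.

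All of this limits the size of the problem. None of it answers the logic: the convention is meant for unknown timing, and here the end date settles the timing.

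A reader might infer more than the documents support:

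- *That events finished before the device was fitted are attributed to the device.* The CGM is one of the two device components and is fitted during selection in all patients (V.4.4). Only the pump is fitted at V1, and only in the investigational group (VI.3.1). Study Emergent is anchored to V1 in both groups, and counting an event as device-related still needs the investigator's causality rating.
- *That selection-period events are mostly CGM-sensor events, so the group comparison is blurred.* The documents give no breakdown of such events.
- *That the chance of a selection-period event falling in V1's calendar month measures the error rate.* That share depends on onset alone. It includes events still ongoing at V1, which an end-date check would not move.

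**Conclusion.** The point holds as a narrow defect. The rule gives a result that contradicts the plan's own definition whenever three things coincide: the start date is unknown or is a partial date that matches V1's year or year and month, the event ended before V1, and the resolution date shows it. In that case the classification is wrong by logic and needs no assumption about rates.

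The practical effect is probably small. The ceiling of about 3.6 points per reclassified patient assumes 28 patients in the group and no other SEAE in that patient. The documents do not support a claim that the safety comparison between groups is materially biased. This is a worthwhile clarification of low priority.

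**What to change.** Add to both branches of the missing-date rule in X.3.5.2: *unless the complete or partial resolution date shows that the AE ended before V1, in which case it is classified as occurring before V1*. Keep the Study Emergent default when the end date is missing or uninformative.

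For programming, a partial end date is informative only if its year, or year and month, is strictly earlier than that of V1. With V1 on 20 June 2022, an end date of May 2022 moves the event to before V1, while an end date of June 2022 with the day missing leaves the default in place.

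The cost is one sentence and one condition in the derivation program, with no new data to collect. If the protocol text itself is edited, XIII.7 requires a signed amendment. Otherwise the change can go into the separate SAP before database lock, with the reason recorded there and in the clinical study report as X.5 requires.
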